7.2. Study Drug Packaging, Labeling, and Storage

Tdap vaccine is supplied as:

- Syringe, without needle, 1 dose - NDC No. 49281-400-89 (not made with natural rubber latex); in package of 5 syringes, NDC No. 49281-400-20.
- Syringe, without needle, 1 dose - NDC No. 49281-400-88; in package of 5 syringes, NDC No. 454 49281-400-15. The tip caps of the prefilled syringes may contain natural rubber latex. No other components are made with natural rubber latex.

Tdap vaccine should be stored at 2° to 8°C (35° to 46°F). DO NOT FREEZE. Product which has been exposed to freezing should not be used. Do not use after expiration date shown on the label.

7.3. Study Drug Preparation

Just before use, shake the vial or syringe well until a uniform, white, cloudy suspension results.

The Tdap vaccine should be a uniform, cloudy, white colored suspension. Parenteral drug products should be inspected visually for particulate matter and discoloration prior to administration, whenever solution and container permit. If either of these conditions exist, the vaccine should not be administered.

When withdrawing a dose from a stoppered vial, do not remove either the stopper or the metal seal holding it in place. Use a separate 25 gauge one-inch sterile needle and syringe for each injection. Using a sterile needle and syringe, withdraw the 0.5 mL dose of vaccine from the single-dose vial and administer the vaccine to the individual.

Changing needles between withdrawing the vaccine from the vial and injecting it into a recipient is not necessary unless the needle has been damaged or contaminated.

Tdap vaccine should not be combined through reconstitution or mixed with any other vaccine.

7.4. Study Drug Administration

Administer Tdap vaccine as a single 0.5 mL intramuscular injection into the deltoid muscle of the upper arm. Do not administer this product intravenously, subcutaneously or intradermally.

Subjects will be vaccinated on Day 1, Month 0, then every 3 months \pm 1 week for 12 months (total of 5 vaccinations). A record of the time, date of administration, NDC number, and lot number of each vaccine will be made in the study source documents and will be reported on an electronic case report form (eCRF).

7.5. Study Drug Accountability and Disposal

Investigational product will be stored and administered at the investigational site by trained personnel. An Investigational Product Accountability Record for this study must be kept current by the clinical site and must contain: dates, quantities, expiration dates and lot number(s) of all investigational product received. Dates, quantities, vial numbers and lot number(s) of investigational product dispensed for each subject will include subject ID and initials of the staff person dispensing the product. The Investigator must account for all product and supplies used in the study. At the end of the study, a final investigational product reconciliation statement must be completed by each site.

Inventory records must be readily available for inspection by the trial monitor and/or auditor, and open to Regulatory Authority inspection or Sponsor/CRO inspection. The Sponsor will keep records regarding shipment, receipt, storage temperature logs, distribution, drug accountability and destruction of the study medication.

8. STUDY PROCEDURES

8.1. Recruitment of Subjects

All subjects will be “Qualified Donors” who have been qualified for continued donations in accordance with Donor Eligibility requirements found in 21 CFR 630.10 and 630.15, and Source Plasma regulations under 21 CFR 640, Subpart G.

8.2. Informed Consent

At the screening visit, candidates will meet with either the site investigator or his/her designee and receive an explanation of the study purpose and requirements. If still interested after receiving an explanation of the study, the candidate will be given an opportunity to review, inquire about, and sign the study informed consent form approved by the IRB. As subjects will also be plasma donors, they will also have been consented to be a plasma donor and have signed and have acknowledged that they have read and understood the site’s “The Automated Plasmapheresis Consent Agreement Form”, the “Dear Donor Facts about HIV Consent”, “The Anti-Tetanus Donation Program Consent Agreement”, and the “Dear Donor Letter” to be sure that the donor is not in a high risk group prohibited from donating plasma.

8.3. Subject Identification

All subjects consented to the study will be assigned a unique subject identification (ID) number. The unique subject ID number will be in the format xyyy composed of the study center number

(x) and subject number (yyy). The subject number will be assigned sequentially beginning with 001 at each site by enrolling the subject into the study with Fast-Track's electronic data management system (EDMS).

8.4. Selection and Withdrawal of subjects

The study population will be composed of healthy plasma donors, male or female, 18 to 63 years of age, inclusive. Donors will have read and understood GCAM / Biomat USA – Grifols “The Automated Plasmapheresis Consent Agreement Form” and the “Dear Donor Facts about HIV Consent” (the agreement that the donor is not in a high-risk group).

8.5. Subject Inclusion Criteria

- Male or female ages 18 to 63 years
- Females of childbearing potential who agree to employ adequate birth control measures during the study
- Signed the informed consent form (ICF)
- Met all of the criteria required by GCAM / Biomat USA – Grifols to be a Normal Source Plasma donor
- Subject is not participating in any other immunization program
- Subject has not had a Tdap vaccination in the last 90 days before the first study vaccination

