4.4. Warnings and Precautions

From the prescribing information ([Sanofi Pasteur-2017](#)):

- For one presentation of Adacel, the tip caps of the prefilled syringes may contain natural rubber latex, which may cause allergic reactions in latex sensitive individuals.
- If Guillain-Barré syndrome occurred within 6 weeks of receipt of a prior vaccine containing tetanus toxoid, the risk for Guillain-Barré syndrome may be increased following a subsequent dose of Tdap vaccine.
- Progressive or unstable neurologic conditions are reasons to defer vaccination.
- Persons who experienced an Arthus-type hypersensitivity reaction following a prior dose of a tetanus toxoid-containing vaccine should not receive Tdap unless at least 10 years have elapsed since the last dose of a tetanus toxoid-containing vaccine.
- Syncope (fainting) can occur in association with administration of injectable vaccines. Procedures should be in place to prevent falling injury and manage syncopal reactions.

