8.6. Subject Exclusion Criteria

- Subject is pregnant
- Subject has a condition or abnormality that in the opinion of the Investigator would compromise the safety of the subject or the quality of the data
- Subject has repeated reactions or hypersensitivity to components in the vaccine (e.g., thimerosal, latex, etc.)
- Subject has history of a severe reaction to any immunization
- Subject has a history of Guillain-Barré Syndrome
- The Investigator concludes that the anticipated vaccination site (deltoid area) is not suitable for AE assessment

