11.2.2. Prior and Concomitant Medications Including Immunizations

Medications being taken by the subject in the 7-day period prior to the first vaccination through the completion of the study will be recorded and reported on an eCRF. The subject's immunization history will also be collected and reported. In general, concomitant medication use is permitted during the study. However, certain medications may require a washout period prior to plasmapheresis and could result in the deferral of a visit or possible removal of the subject from the study. In addition, immunosuppressive drugs will be prohibited as these can attenuate antibody responses. Epinephrine will be available on site for the treatment of possible anaphylaxis reactions. Subjects will be asked to record medication use to treat an AE in their diary. The name of the medication, start date, stop date or ongoing, dose, route and frequency will be recorded on a source document at study visits and will be reported on an eCRF.

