5.3. Baseline and Other Assessments

A complete medical history and demography (gender, age, race, and ethnicity) will be collected at the screening visit. Medications being taken by the subject in the 7-day period prior to the first vaccination through the completion of the study along with complete immunization history will be recorded and reported on an eCRF.

Vitals signs, full physical examinations and hematocrit and total protein determinations as part of the routine plasmapheresis will be assessed during pre-donation screening.

Infectious disease testing will be performed on all plasma samples collected from plasma donations and if a subject is positive for any of these infectious diseases, they will be taken off study. In addition, RPR (syphilis test) is performed every 4 months. If the subject is a first time donor, they must have two sequential plasma donations that are negative for the following infectious diseases to be eligible for plasmapheresis: Anti-HIV-1/2, HBsAg, Anti-HCV, SPE/RPR, Indirect Coombs, and PCR testing for HIV-1, HBV and HCV, HAV, and Parvovirus B19.

An eligibility checklist will be completed at screening. If the subject is not eligible for the study, a Reasons Not Eligible eCRF will be completed.

A dipstick urinalysis will be performed that tests for protein, blood, leukocyte esterase, nitrates, pH, specific gravity, ketones, bilirubin, and glucose. A blood sample will also be collected for a serum creatinine test. These tests will be performed to monitor for the possible development of immune complex-mediated glomerular disease.

Anti-diphtheria antibody levels will be measured at a central laboratory using the EUROIMMUN Anti-Diphtheria Toxoid ELISA (IgG). High anti-diphtheria titers will be assessed for an association with an increase in reactogenicity.

6. Hypotheses to be Tested

Hypothesis tests will be performed in order to determine if there is an association between reactogenicity and anti-diphtheria titers. Null Hypothesis of no association between reactogenicity and anti-diphtheria titers will be tested on Slope obtained using simple linear regression analysis at alpha=0.01 using two-sided tests.

7. Sample Size

One hundred subjects will be enrolled in this study.

8. Data Quality Assurance

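### The 90-day limit before dose 1 names Tdap only, although the titers measured also respond to other tetanus- or diphtheria-toxoid vaccines, and no SAP rule identifies donors who recently had one

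*Protocol*

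**What the plan says.** Protocol 8.5 requires: "Subject has not had a Tdap vaccination in the last 90 days before the first study vaccination". No other rule in 8.5, 8.6, 8.7 or 11.2.2 sets a look-back period for a vaccine. The neighbouring criterion is "Subject is not participating in any other immunization program". Protocol 8.6 also has a discretionary exclusion, but it turns on a condition or abnormality, not on a recent vaccination.

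Protocol 11.2.2 adds that "The subject's immunization history will also be collected and reported". Table 4 schedules the immunization record at screening only. SAP 9.4 puts prior immunizations in a by-subject listing and gives them no further use.

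On outcomes, Protocol 11.1 and 11.2.7 specify IgG assays against tetanus toxoid and diphtheria toxoid. Titers are drawn at screening (Day -7 to -1) and, under Protocol 8.8, not at Month 0. On the second antibody, SAP 5.3 says: "High anti-diphtheria titers will be assessed for an association with an increase in reactogenicity". SAP 9.5 tests this with a simple linear regression without covariates and with 2x2 tables that define a high titer by the 75th or 90th percentile.

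**The concern.** The limit is written for one product type, while the assays read antibody to two toxoids whatever product induced it. A donor given a single non-Tdap booster elsewhere, for example after a wound, two weeks before dose 1 meets every criterion listed in the protocol. For that donor, dose 1 follows the previous toxoid by days or weeks. The documents require 90 days after Tdap and 3 months ± 1 week between study doses.

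Three outputs could be affected:

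- the screening row of SAP Tables 13-15, which is the only titer before any study dose;
- the dose 1 columns of the adverse event and solicited-event tables, which serve the primary objective;
- the dose 1 block of the reactogenicity-by-titer table (SAP Table 11) and the matching regression.

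A non-study toxoid dose during the 18 months would also raise later titers that the summaries attribute to the 3-monthly schedule.

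**Working it through.** The plan has no figure of its own to reproduce: N = 100 is stated without a power or precision basis. The check is first textual, then a sizing on stated assumptions.

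**1. Does any text close the gap?**

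- The other-program criterion (Protocol 8.5) has no look-back period and does not naturally cover one past dose.
- Immunization history is collected, but the only rule it can be checked against is the Tdap one.
- The ITT set (SAP 4) is every enrolled subject who received any product. The per-protocol set is five doses plus the 6-month visit. Neither removes the donor.
- The regression has no covariates (SAP 9.5).

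The listed criteria and the analysis rules therefore leave the donor in and unmarked.

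**2. Which output is affected depends on timing.** Screening is Day -7 to -1. A toxoid dose before that draw, with time for a response, can raise the screening titer. A dose after the draw leaves the screening titer alone but can affect dose 1 adverse events and the Month 1-3 titers. Some carry-over of reactions into the 3-day solicited window is plausible, since Protocol 4.5 reports reactions to Adacel over Days 0-14. Applying that window to another toxoid vaccine is an assumption.

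**3. Screening GeoMean.** If a fraction f of donors has a titer raised k-fold, the mean log titer rises by f × ln k, so the GeoMean is multiplied by k^f. The documents give neither f nor k; both are assumed.

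| Share affected | 2-fold rise | 4-fold rise |
|---|---|---|
| 1% | 2^0.01 = 1.007 | 4^0.01 = 1.014 |
| 2.5% | 2^0.025 = 1.017 | 4^0.025 = 1.035 |
| 5% | 2^0.05 = 1.035 | 4^0.05 = 1.072 |
| 10% | 2^0.10 = 1.072 | 4^0.10 = 1.149 |

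The 2.5% row corresponds to one toxoid dose per donor every 10 years: 90/3650 = 2.5% fall in a 90-day window, before removing Tdap doses. For scale, with an assumed natural-log SD of 1, the 95% interval on a GeoMean of 100 donors is exp(±1.96 × 1/√100), a factor of 0.82 to 1.22.

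**4. Dose 1 event rates.** Each affected donor moves any dose 1 incidence by at most 1/100, or 1 percentage point.

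**5. High-titer cells.** With 100 donors, the high group is about 25 (75th percentile) or 10 (90th percentile). If the affected donors all fall there:

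- one donor is 1/25 = 4% or 1/10 = 10% of the group;
- five donors are 5/25 = 20% or 5/10 = 50%.

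The SAP does not say which visit's titer enters the dose 1 analysis. The screening value is likely, but that is an inference.

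**6. Chance of at least one such donor.** With assumed prevalence p, this is 1 - (1 - p)^100: 39% at p = 0.5%, 63% at 1% and 87% at 2%.

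**The case against.** The best defence is that the rule targets the exposure these centers create. Donors sign "The Anti-Tetanus Donation Program Consent Agreement", and Protocol 13.5 treats the first Tdap dose as a standard procedure, so recent Tdap is the obvious risk and the other-program criterion covers organized schemes. The protocol never says that the 90 days is meant to protect the baseline titer. This is fair, but it does not cover a single booster given elsewhere.

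Several stronger readings are tempting, and the documents do not support them:

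- **That the rise in titer is understated.** No fold-rise, change-from-baseline or seroresponse endpoint is defined (Protocol 9.1, SAP 3.3). Screening is a descriptive row; the issue is only how a reader compares it with later rows.
- **That a dose given days before dose 1 necessarily distorts the screening titer.** It may fall after the draw, or too close to it to matter.
- **That nothing guards against a toxoid dose during the study.** It is true that "In general, concomitant medication use is permitted during the study". But eligibility is rechecked before every vaccination, medications are recorded to study completion, medical history is updated at each visit, and staff ask about medically attended events. Capture is largely in place. However, the 90-day criterion refers to the first study vaccination, and no analysis rule follows from what is captured.
- **That the warnings show a wider intended washout.** The phrase "elapsed since the last dose of a tetanus toxoid-containing vaccine" in Protocol 4.4 comes from a label precaution about prior Arthus-type reactions. It shows that the wider class has a name, not that the limit was meant to cover it.
- **That such a donor is certain to be enrolled.** The sponsor's source plasma criteria and the donor regulations cited in Protocol 8.1 and 8.5 are not in the documents and might defer some donors.

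A last objection is that a correctly measured high titer is the predictor under study, not contamination. That stands for the titer itself. It does not cover reactions carried over from another vaccine, or a titer drawn before a booster that preceded dose 1.

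**Conclusion.** The gap in wording and analysis is real. Protocol 8.5 limits prior Tdap only, the assays respond to a wider class, and no SAP rule identifies a donor with a recent non-Tdap toxoid dose.

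The likely effect is small for most outputs. Assuming 1-10% of donors affected and a 2- to 4-fold titer rise, the screening GeoMean moves by about 1% to 15%, and at 2.5% affected by only 1.7% to 3.5%. The high-titer 2x2 cells are the exception, because a few donors can be a large share of about 25 or 10. All of this rests on an assumed frequency and rise, and the cell calculation also assumes that affected donors land in the high group. For doses received during the study, what is missing is mainly an analysis rule, not data capture. This is a cheap improvement, not a flaw that threatens the trial's conclusions.

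**What to change.** 1. In Protocol 8.5, reconcile the scope of the limit with the antibodies measured: name the class of tetanus- or diphtheria-toxoid-containing vaccines, leave the stated 90 days unchanged, and check the criterion against the immunization record already collected at screening.
2. In SAP 4, 9.5 and 9.7, flag any recent or on-study non-study tetanus- or diphtheria-toxoid dose. Leave titers after an on-study dose out of the per-protocol titer summaries. Repeat the dose 1 reactogenicity analysis and the titer summaries without flagged donors.

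The cost is one line in the criterion and its checklist, a short SAP addition and a little more programming. No new visit or assay is needed. The downside is that a few donors are delayed or screened out. If enrollment is already complete, the second step can still be done from the recorded history and medications.

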8.6. Subject Exclusion Criteria

- Subject is pregnant
- Subject has a condition or abnormality that in the opinion of the Investigator would compromise the safety of the subject or the quality of the data
- Subject has repeated reactions or hypersensitivity to components in the vaccine (e.g., thimerosal, latex, etc.)
- Subject has history of a severe reaction to any immunization
- Subject has a history of Guillain-Barré Syndrome
- The Investigator concludes that the anticipated vaccination site (deltoid area) is not suitable for AE assessment

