8.8. Procedures Performed on Vaccination Days

Procedures on vaccination days and at the next visit within 1 to 3 days after each vaccination at Months 0, 3, 6, 9, and 12 unless otherwise noted will be performed in the following order:

- Pre-donation screening examination (see [Table 4](#)). Review of diary card and open ended question for AEs (not performed at Month 0); however, explanation of the use of the diary card will be performed at the Month 0 visit
- Confirm eligibility for plasmapheresis
- Perform plasmapheresis and collect plasma sample for anti-tetanus and anti-diphtheria antibody titer tests (not performed at Month 0) and plasma for infectious diseases
- Administer vaccine (ensure that all study participants continue to meet study eligibility criteria prior to each vaccination)
- Closely observe study participants for 30 minutes after each vaccination for immediate adverse reactions per standard practice
- Query subject about AEs before leaving the center
- Perform a dip-stick urinalysis and serum creatinine from 1 to 3 days after each vaccination. If the subject does not return to the center within this time frame, the sample should be collected and tested at the next visit to the center (typically within one week for the next plasma donation).

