8.11. Subject Withdrawal Criteria

A subject can withdraw from the trial at any time. The subject should contact the Investigator immediately and notify him/her that they are leaving the study. If possible, the reason for withdrawal for all subjects who do not complete the 12-month treatment period will be recorded.

The Investigator may withdraw a subject from the study in the following cases:

- For safety reasons, such as a severe or serious AE, that does not justify continuation in the study in the opinion of the Investigator;
- For a protocol violation that jeopardizes the performance of the study;
- The subject does not comply with the protocol;
- The subject no longer qualifies as a plasma donor;
- Continued participation will pose a risk to the subject; or,
- Pregnancy.

In the event of subject withdrawal, site personnel should attempt to collect the subject's study diary (completed through the day of withdrawal, if available).

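### The protocol does not state whether a severe reaction to one study dose bars the next, and SAP Tables 6-9 do not separate the resulting selection from a true change by dose

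*Protocol*

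**What the plan says.** **Eligibility for a dose.** Protocol section 8.6 lists as an exclusion "Subject has history of a severe reaction to any immunization", with no time limit and no definition of severe. It also excludes a subject where "Subject has repeated reactions or hypersensitivity to components in the vaccine", and any condition that the Investigator thinks would compromise safety or data quality. Section 8.8 tells staff, before giving vaccine, to "ensure that all study participants continue to meet study eligibility criteria prior to each vaccination". Table 4 footnote a repeats the re-check and provides a Reasons not Eligible for Vaccination eCRF.

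**Withdrawal from the study.** Section 8.11 says the Investigator may withdraw a subject "For safety reasons, such as a severe or serious AE, that does not justify continuation in the study in the opinion of the Investigator".

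**Precautions.** Section 4.4 reports, from the prescribing information, that people with a prior Arthus-type reaction to a tetanus toxoid vaccine "should not receive Tdap unless at least 10 years have elapsed since the last dose of a tetanus toxoid-containing vaccine", and that "Progressive or unstable neurologic conditions are reasons to defer vaccination". Neither is named in 8.6. Latex and Guillain-Barré syndrome, also in 4.4, are.

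**Analysis.** Five doses are planned: "Subjects will be vaccinated on Day 1, Month 0, then every 3 months" (section 7.4). SAP Tables 6-9 report AEs in one column per vaccination number plus an overall column. Each column has its own N, but no denominator rule is given.

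**The concern.** Safety of dosing every 3 months is the primary objective, so whether a subject who reacts receives the next dose is central to the trial. Read literally, 8.6 with 8.8 turns a severe reaction to one dose into a bar on the next. Section 8.11 contemplates continuing after a severe AE. Two careful readers could decide differently for the same subject.

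The decision also shapes the main safety tables. A natural way to judge repeat dosing is to read across columns 1 to 5. If subjects who reacted are not re-dosed, later columns describe a selected group, and a flat or falling rate could be taken as good tolerance. A reader of the tables could not tell how much of the pattern is selection.

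**Working it through.** **1. The sections side by side**

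| Question | 8.6 + 8.8 + Table 4 footnote a | 8.11 | 4.4 |
|---|---|---|---|
| What is decided | Eligibility for the next dose | Staying in the study | Background from the label |
| Force | Mandatory re-check | Investigator may withdraw | Not written as a study rule |
| Severe reaction on study | Barred, if it counts as history | Investigator's opinion | Silent on severe reactions in general |
| Arthus-type reaction | Not named; hypersensitivity bullet might apply | Not named | 10-year interval |
| Progressive or unstable neurologic condition | Not named; Investigator-opinion bullet might apply | Not named | Reason to defer |

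Three things are left open: whether a reaction during the trial is history, whether a severe reaction means the severe AE grade, and which section governs. The second matters because section 11.2.8.1.5 says that a severe AE can be clinically minor and gives headache as its example.

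**2. Size of the selection (illustration)**

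The plan gives no figure to reproduce. SAP section 7 says only "One hundred subjects will be enrolled in this study". Inputs: severe headache p = 2.8% (protocol Table 3: one dose, days 0-14); four doses after which a later dose can be lost. Assumptions: the same p applies at each dose, and every severe headache disqualifies.

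- Chance that the question arises at dose 1 among 100 subjects: 1 - 0.972^100 = 94.2%.
- Independent reactions: 1 - (1 - 0.028)^4 = 1 - 0.8926 = 10.7% lose at least one later dose.
- Fully clustered (the same people always react): all are found at dose 1, so 2.8% lose later doses.

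The number lost and the distortion of the rate move in opposite directions. Under independence the most subjects are lost, but the severe rate among those re-dosed stays at 2.8%. Under full clustering few are lost, but the rate falls to 0% from dose 2 with no change in reactogenicity.

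For cases in between, use a beta-binomial model with within-subject correlation r: s = 1/r - 1, a = ps, b = (1 - p)s. The dose 5 rate among those never excluded is a/(a + b + 4). For r = 0.3: s = 2.333, a = 0.0653, b = 2.268, so the rate is 0.0653/6.333 = 1.03%. The share remaining is the product of (b + i)/(a + b + i) for i = 0 to 3, that is 0.9720 × 0.9804 × 0.9849 × 0.9878 = 92.7%.

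| Correlation | Still eligible at dose 5, of 100 | Severe rate at dose 5 (2.8% at dose 1) |
|---|---|---|
| 0 | 89.3 | 2.8% |
| 0.1 | 90.6 | 1.94% |
| 0.3 | 92.7 | 1.03% |
| 0.5 | 94.3 | 0.56% |
| 1 | 97.2 | 0% |

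**3. Common events**

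Any injection-site pain is 65.7% (protocol Table 2). Remove 10.7 of 100 subjects and assume that all of them had pain: (65.7 - 10.7)/(100 - 10.7) = 55.0/89.3 = 61.6%. The shift is about 4 points under an unfavourable assumption.

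**4. What the SAP outputs would show**

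Table 1 gives reasons for early termination, Table 4 attendance and number of doses, Listing 8 the doses given, and Listings 11 and 13 the action taken and AE withdrawals. Listing 2 covers screen failure only. SAP section 9.1 promises listings of all data, but no table or listing shell carries the reasons from the Reasons not Eligible for Vaccination eCRF.

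**The case against.** The strongest reply is that the sections do not conflict. Sections 8.6 and 8.8 decide the next dose and have their own form; 8.11 decides study withdrawal and uses the Subject Disposition form. A subject can miss a dose and stay in follow-up. SAP section 5.1 allows study drug to be interrupted as well as discontinued, and the ITT population needs only one dose. A reader might infer that the protocol gives flatly contradictory answers; on this point the reply succeeds, because the texts are compatible. What survives is that no section states this reading (section 11.2.5 treats continued eligibility and withdrawal together) and that the key terms are undefined.

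A reader might also infer that 4.4 gives a third answer, or that a moderate Arthus-type reaction would pass the re-check. The documents do not support either. Section 4.4 says nothing about severe reactions in general. For an Arthus-type reaction on study, its 10-year interval and an exclusion under 8.6 lead to the same result within a 12-month schedule. The hypersensitivity bullet has no severity threshold, and the Investigator-opinion bullet is broad. These might catch such cases; the gap is that the precautions are not named.

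It is also fair that the trial recruits at one site, that a medical monitor follows AE trends and can recommend individual discontinuations, and that attrition is partly visible from the column Ns and listings. That reduces the practical risk. It does not give the reader the reasons for withheld doses or a like-for-like comparison across columns.

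**Conclusion.** The ambiguity is real and bears on the primary objective, but it is a gap in wording and not a proven contradiction. It should be fixed; it does not invalidate the design.

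The selection problem is separate. It arises under any rule that stops re-dosing, so clarifying the text alone would not remove it. Its size depends on assumptions the documents cannot settle: 2.8% to 10.7% of subjects would lose a later dose if every severe headache counted. The dose 5 severe rate could lie anywhere from 0% to 2.8% with no true change, depending on how far reactions cluster within people. If only narrower events count, fewer doses are lost; if no subject is stopped, none are.

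A reader might conclude that later columns would hold only tolerant subjects. That holds only under full clustering with the strict reading; at any lower correlation some subjects prone to react remain. A reader might also add the severe rates for pain, headache, body ache, fatigue, chills, joints, nausea and vomiting (8.9% in all) and reach 31.1% losing a dose. That sum ignores overlap between symptoms in the same person, and no section says that each such event disqualifies.

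**What to change.** 1. **Protocol.** The sponsor reconciles 4.4, 8.6, 8.8 and 8.11 so that one stated rule governs re-vaccination after an on-study reaction. It should say whether such a reaction counts as history, what severe means there, and how withholding a dose relates to study withdrawal. The Arthus-type and neurologic precautions in 4.4 should be reflected in the re-checked criteria, or their omission explained. The sponsor's medical team decides the content.

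2. **SAP Tables 6-9.** State that each column's N is the number who received that dose. For each dose column add (a) the dose 1 rate in the same subjects who received that dose, and (b) the number not re-dosed, with reasons from the Reasons not Eligible for Vaccination eCRF. For an event that itself bars re-dosing, row (a) is zero by construction. It therefore exposes the selection without correcting it, and must be read beside row (b) and the full dose 1 rate.

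The cost is a protocol clarification and slightly longer tables, from data already collected.
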